## 6. Study Calendar

Survey is collected at baseline. See below for number of questions in the study assessment.

Table 3	Baseline
Participant questionnaires	(min/max # questions based on skip pattern)
Sociodemographics	Max 3q*
Insurance and COVID-related change	Min 4q/ Max 8q
Distance traveled for mammogram	Max 1q
Reason for refusing to participate in TMIST	Max 1q
Employment and COVID-related change	Max 2q
Financial situation and COVID-related change	Max 7q
COVID testing or infection	Max 2q
Participant reported COVID-related delays in care	Min 3q/Max 4q
COVID-specific distress	Max 10q
Change in smoking and alcohol use	Max 2q
Preference for delaying screening due to COVID	Max 1q
Perceived susceptibility to disease	Max 2q
PROMIS-10 Overall quality of life	Max 10q
PROMIS ASF	Max 4q
PROMIS DSF	Max 4q
Assistance needed questions	Min 1q/Max 3q
Minimum/Maximum number of items	Min 57q/64q

\*Some of the sociodemographic questions are collected at registration and entered into the OPEN database and not listed here.

## 7. Statistical Considerations

### 7.1 Study Design and Objectives

#### 7.1.1 Primary Objectives

In a population of women who decline participation in TMIST (EAQ201 participants), we will compare the proportion of WOC vs non-WOC with respect to who experience COVID-related financial hardship, a composite endpoint defined as any psychological response (financial distress, food/housing insecurity) or change in their material condition.

Hypothesis: Compared to non-WOC, WOC will experience more COVID-related financial hardship.

#### 7.1.2 Secondary Objectives

7.1.2.1 Compare the proportions of WOC vs non-WOC EAQ201 participants with COVID-related change in their material condition, a composite measure.

Hypothesis: Compared to non-WOC, WOC will experience more COVID-related change in their material condition.

7.1.2.2 Compare the proportions of WOC vs non-WOC EAQ201 participants with COVID-specific perceived financial distress.

Hypothesis: Compared to non-WOC, WOC will experience more COVID-specific perceived financial distress.

7.1.2.3 Compare the proportion of WOC in TMIST participants vs EAQ201 participants.

Hypothesis: The proportion of WOC should be higher in the TMIST decliners than that in TMIST agree-ers.

#### 7.1.3 Exploratory Objectives

7.1.3.1 Compare the proportion of WOC vs non-WOC EAQ201 participants with COVID-related employment change, a composite measure.

7.1.3.2 Compare the proportions of WOC vs non-WOC EAQ201 participants with COVID-specific perceived distress and perceived susceptibility to COVID and breast cancer.

7.1.3.3 Compare the proportions of WOC vs non-WOC EAQ201 participants with relative increase in smoking and alcohol use, risk factors for breast cancer.

7.1.3.4 Compare participant-reported quality of life, anxiety and depression between WOC and non-WOC EAQ201 participants.

7.1.3.5 Assess the effects of sociodemographic characteristics, and federal-, state- or local-level COVID-19 factors on TMIST participation, in WOC vs non-WOC.

7.2 Primary Objective

The primary objective is to compare the proportion of WOC EAQ201 participants who experience COVID-related financial hardship vs non-WOC EAQ201 participants. The results, with and without adjustment for missing values (see [7.5](#)), will be compared as a sensitivity analysis. Logistic regression models, with and without stratification by WOC status, will be fit with financial hardship as the response variable to investigate other sociodemographics (e.g., age, marital status, insurance status) and state- and local-level factors (e.g., state COVID severity, shelter-in-place policies, state and local unemployment during shelter-in-place) as moderators.

Sample Size Considerations for the Primary Objective ([7.1.1](#)):

The primary objective is to compare the proportion of WOC EAQ201 participants who experience COVID-related financial hardship (see **Table 1** for definition) with the proportion of non-WOC EAQ201 participants who experience COVID-related financial hardship. The National Bureau of Economic Research estimated unemployment rates by race and ethnicity in April 2020, around shelter-in-place regulations. Unemployment in African-American and Latinx populations averaged 18% compared to Whites (13%). At a sample size of 1000 women who decline TMIST participation, we expect to recruit at least 10-25% WOC into this study. Assuming alpha of 0.05, we estimated power over a range of differences across various proportions (see **Table 4**). For instance, at a sample size of 1000 with 10% of WOC, we have 77% power to detect a minimum difference of 0.10 between two proportions (0.2 vs. 0.1); at a sample size of 1000 with 25% of WOC, we have 88% power to detect a minimum difference of 0.08 between two proportions (0.18 vs. 0.1). Please note that based on DCP-001, 16% of the women who declined TMIST were WOC. Accrual onto TMIST is expected to continue for another 4.4 years. Also based on DCP-001 and extrapolating to the Non-NCORP US sites, accruing 1,000 women to this study is achievable. We do not envision any danger that this study will close due to lack of accrual.

**Table 4: Estimated power for a two-sample proportions using Fisher's Exact test (two-sided). N1: # of WOC; N2: # of non-WOC**

Sample size (N)	N1/N2	P1 (WOC)	P2 (non-WOC)	Delta	Alpha	Power
(Sample size: 1000; N1/N2=1/9, i.e.,10% of WOC)						
1000	1/9	0.200	0.100	0.100	0.05	0.77
1000	1/9	0.225	0.100	0.125	0.05	0.90
1000	1/9	0.250	0.100	0.150	0.05	0.96
1000	1/9	0.250	0.150	0.100	0.05	0.66
1000	1/9	0.275	0.150	0.125	0.05	0.83
1000	1/9	0.300	0.150	0.150	0.05	0.92
(Sample size: 1000; N1/N2=1/3, i.e.,25% of WOC)						
1000	1/3	0.180	0.100	0.080	0.05	0.88
1000	1/3	0.200	0.100	0.100	0.05	0.97
1000	1/3	0.220	0.100	0.120	0.05	0.99
1000	1/3	0.230	0.150	0.080	0.05	0.79

1000	1/3	0.250	0.150	0.100	0.05	0.92
1000	1/3	0.270	0.150	0.120	0.05	0.98

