## 5. Methodology Plan

We will conduct an observational study to compare 1) the proportion of COVID-related participant factors (including financial hardship and distress among WOC who decline participation in TMIST (EAQ201 participants) compared to non-WOC EAQ201 participants; and 2) effects of federal-, state- and local-level COVID-19 factors on TMIST participation, in WOC vs non-WOC. The primary objective compares COVID-related financial hardship between WOC vs non-WOC EAQ201 participants (see **Table 1** definition). Federal-, state-, local-, practice- and participant-level moderators (see Fig. 1 conceptual model) will be evaluated with hierarchical regression models. For the exploratory objectives, we will compare the effects of federal-, state- and local-level COVID-related factors on TMIST participation (secondary outcome), stratified by WOC vs non-WOC. Any woman 45-74 years old who is scheduled for breast cancer screening and is eligible for TMIST but declines will be approached by the TMIST site research associates (RAs). Enrollment for TMIST typically occurs immediately prior to the scheduled breast screening visit. Solicitation for participation in EAQ201 will occur at the same time for those who decline TMIST. TMIST site RAs will ask women who decline TMIST if they are interested in participating in EAQ201.

Sites participating in the parent study may approach potential participants using written materials, by phone or at the time of screening mammography. We will use the same enrollment processes. For those who are approached by phone and who decline to participate in TMIST will be recruited for EAQ201 during the same call.

For those sites that use the written materials, it is up to the participant to actively respond to the site at which point they are additionally screened for eligibility for TMIST, usually by phone. Among those who respond to written materials and are additionally screened by phone, we will be able to approach the women who decline to participate in TMIST for EAQ201 recruitment.

Paper documentation of consent is required. It may be signed when the participant attends the scheduled screening mammogram.

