### 7.4 Assess the effects of sociodemographic characteristics, and federal-, state- or local-level COVID-19 factors on TMIST participation, in WOC vs non-WOC.

For the exploratory objective ([7.1.3.5](#)), we will compare the effects of sociodemographic characteristics, federal-, state- or local-level factors (e.g. maximum number of COVID-19 cases, state unemployment during shelter-in-place, local unemployment during shelter-in-place) on TMIST participation, stratified by WOC vs non-WOC. We will fit a logistic regression model with TMIST participation status (EAQ201 participant or TMIST participant) as the response variable to investigate other sociodemographic (e.g., marital status, neighborhood SES, insurance type), federal-, state- or local-level factors (see **Table 2**). Regression modeling will be conducted with and without stratification by WOC vs non-WOC.

The analysis set will include the 1000 EAQ201 participants from this study and a corresponding number of TMIST participants, who will be randomly selected from the enrolled participants in the main TMIST study. The selection will be stratified by site and enrollment time. Assuming that the proportion of overall EAQ201 participants is from 0.20 to 0.50, **Table 5** below shows the power analysis of testing for the odds ratio in the logistic regression. The variables of interest can be continuous or categorical (binary). For instance, 2000 women (1000 EAQ201 participants versus 1000 randomly selected TMIST participants) achieves 90% power at a 0.050 significance level to detect a change in the proportion of EAQ201 participants from 0.50 at the mean of the testing variable to 0.538 when the value of the variable is increased to one standard deviation above the mean. This change corresponds to an odds ratio of 1.165. An adjustment was made since a multiple regression of the independent variable of interest on other independent variables in the logistic regression obtained an R-Squared of 0.10.

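### Sections 7.2 and 7.4 do not carry Section 5's hierarchical models into their logistic regressions, and Table 5 treats women as independent even for state- and local-level factors

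*Combined protocol and SAP*

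**What the plan says.** Section 5 (Methodology Plan), directly after describing the primary comparison, commits to a multi-level structure: "Federal-, state-, local-, practice- and participant-level moderators (see Fig. 1 conceptual model) will be evaluated with hierarchical regression models".

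Section 7.2, which specifies that analysis, describes it as follows: "Logistic regression models, with and without stratification by WOC status, will be fit with financial hardship as the response variable". The covariates include "state- and local-level factors (e.g., state COVID severity, shelter-in-place policies, state and local unemployment during shelter-in-place) as moderators". It names no random effect, generalized estimating equation, cluster-robust variance or clustering level.

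For the participation outcome, Section 5 says "For the exploratory objectives, we will compare the effects of federal-, state- and local-level COVID-related factors on TMIST participation", and that sentence names no hierarchical model. Section 7.4 says "We will fit a logistic regression model with TMIST participation status (EAQ201 participant or TMIST participant) as the response variable", with federal-, state- and local-level factors among the covariates. The comparators are a random sample of TMIST participants: "The selection will be stratified by site and enrollment time". The allocation within those strata is not given.

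On power, Section 7.4 states that "2000 women (1000 EAQ201 participants versus 1000 randomly selected TMIST participants) achieves 90% power at a 0.050 significance level" for an odds ratio of 1.165 per standard deviation. The only adjustment described is an R-squared of 0.10 for correlation among covariates.

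**The concern.** State COVID severity, shelter-in-place policy and state unemployment take one value for every woman in a state, and women are also grouped by site. Section 5 sets no cap on enrollment at any one site, so clusters may be large and unequal. If hardship varies between states for reasons outside the model, women in the same state do not supply independent evidence about a state-level factor. A logistic model that ignores this reports standard errors that are too small for that factor.

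Section 5 recognizes the structure, but the statistical section does not say how it enters the model or the power calculation. The study lists several state burden and policy measures and intends its results to inform later intervention trials. A state factor declared important on standard errors that are too small would mislead that work.

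**Working it through.** **1. Table 5 reproduced.** For Table 5A under independence, N = (z₀.₉₇₅ + z₀.₉₀)² / [P0(1−P0) · ln(OR)² · (1−R²)]. Row 1: (1.96 + 1.2816)² / [0.25 × 0.02332 × 0.9] = 10.51 / 0.00525 ≈ 2002, against 2000 stated. The six rows give 2002, 2995, 3507, 5254, 5960 and 9040, against 2000, 3000, 3500, 5250, 6000 and 9000. Table 5B also reproduces within 3% with the corresponding binary-covariate formula. No clustering allowance is built in.

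**2. Row 1 of Table 5A for a factor constant within state.** Take equal state sizes m = 2000/(number of states), an observed-scale ICC, and comparators not matched 1:1 within site. Then DE = 1 + (m−1)·ICC and power = Φ(3.2415/√DE − 1.96). The ICC and the number of states are assumptions here and in every step below.

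| States | ICC 0.01 | ICC 0.02 | ICC 0.05 |
|---|---|---|---|
| 20 (m = 100) | DE 1.99, power 0.63 | DE 2.98, power 0.47 | DE 5.95, power 0.26 |
| 30 (m = 66.7) | DE 1.66, power 0.71 | DE 2.31, power 0.57 | DE 4.28, power 0.35 |

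The stated power is 0.90.

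**3. Section 7.2, state-level main effect.** Simulated type I error of the unclustered Wald test, with 1,000 women, 15% hardship, unequal state sizes, a null state factor and 1,500 replicates per cell:

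| States | latent ICC 0.01 | 0.02 | 0.05 |
|---|---|---|---|
| 20 | 9% | 13% | 21% |
| 30 | 7% | 9% | 16% |

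Across all the set-ups run with 20 to 30 states, the range is 6.5% to 26%. At ICC 0 it is about nominal (5% to 6%).

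A formula check needs the ICC on the observed scale: approximately p(1−p) · [ρ/(1−ρ)] · π²/3. At p = 0.15, latent 0.01, 0.02 and 0.05 become 0.0042, 0.0086 and 0.0221. With 20 states of 50 women, DE = 1.21, 1.42 and 2.08, and 2[1−Φ(1.96/√DE)] gives 7.4%, 10.0% and 17.4%. With 30 states of 33.3 women, DE = 1.14, 1.28 and 1.71, giving 6.6%, 8.3% and 13.4%. The formula assumes equal state sizes, and unequal sizes push the error higher.

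**4. Within WOC strata.** Take the 16% WOC share of decliners in Section 7.2, 20 equal states and an observed-scale ICC of 0.02. The non-WOC stratum has 840/20 = 42 women per state, so DE = 1 + 41 × 0.02 = 1.82 and the error is about 15%. The WOC stratum has 160/20 = 8 per state, so DE = 1 + 7 × 0.02 = 1.14 and the error is about 7%. The two strata would carry different error rates, which distorts an informal comparison between them.

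**5. WOC-by-state-factor interaction.** Simulated error was 4% to 6% in every random-intercept scenario, and 5% in the one scenario with a random WOC slope.

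**6. Section 7.4.** If each site contributes equal numbers of EAQ201 and TMIST women, the EAQ201 proportion is 0.5 in every site, and hence in every state. The log-odds are 0 everywhere, so the pooled coefficient of a state-level factor, with no other covariates, is exactly 0. Simulation gave 0% rejection even with a true odds ratio of 1.165.

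If comparators are not matched to decliners by site (2,000 women, 800 replicates), simulated error at ICC 0.01, 0.02 and 0.05 was 15%, 28% and 44% with 20 states, and 16%, 21% and 38% with 30 states. At ICC 0 it was 4% and 5.5%.

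**7. Primary comparison.** All 12 rows of Table 4 reproduce within 2 points by exact Fisher power (for example 0.777 against 0.77, and 0.886 against 0.88). That comparison contains no state-level factor.

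**The case against.** The strongest reply is that nothing conflicts. Logistic describes the outcome and link, hierarchical describes the structure, and a hierarchical logistic model satisfies Sections 5 and 7.2 together. Neither 7.2 nor 7.4 says that the model is unclustered. This stands: a reader might infer a flat contradiction, but the documents support only under-specification that the two sections leave unreconciled. It is weaker still for 7.4, because Section 5's sentence on participation promises no hierarchical model. What remains is that an analyst could follow Section 7 to the letter, fit an unclustered model and break no stated rule.

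Second, the size rests on two assumed inputs, and with no between-state variation there is no inflation. That also stands. However, the study itself hypothesizes that state-level factors act on these outcomes, so planning on zero between-state variation is hard to defend.

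Third, a reader might infer that the effective sample size for a state factor is close to the number of states. It is not under these assumptions. With 1,000 women and an observed-scale ICC of 0.01 to 0.05, N/DE is 671 down to 290 for 20 states and 756 down to 382 for 30.

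Fourth, a moderator test in the strict sense is an interaction, and that was near nominal in the scenarios run. This is conceded. But 7.2 names no interaction term. It names pooled and WOC-stratified models, whose state-level coefficients are main effects.

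Fifth, the site-stratified selection in 7.4 means that false positives cannot simply be assumed there. This is also conceded: the documents do not say which of the two cases applies.

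**Conclusion.** The point holds as an unreconciled specification with a real but conditional consequence. Table 5's 90% power cannot be read as applying to state-constant factors if there is any between-state variation. For 7.2, an unclustered fit would give about 7% to 26% type I error for state-level main effects, conditional on an assumed latent ICC of 0.01 to 0.05 and 20 to 30 states, and about 5% at ICC 0.

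For 7.4 the direction is open. One-to-one selection within site makes state main effects non-estimable; any other allocation can inflate false positives. A claim that 7.4 will produce false positives goes further than the documents allow, as does a claim that the WOC-by-state interaction is inflated. The affected analyses are the supporting models in 7.2 and one exploratory objective (7.1.3.5). The primary WOC versus non-WOC comparison stands.

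**What to change.** - **Section 7.2:** specify mixed-effects logistic regression with random intercepts for state and site, or cluster-robust errors with a small-cluster correction. Base the reference degrees of freedom for state-level terms on the number of states.
- **Section 7.4:** state how many TMIST comparators are drawn per decliner within each site and time stratum, and account for the site strata in the model. If selection is 1:1 within site, state that state-level main effects are not estimable; random intercepts would not recover them.
- **Table 5:** state that the power applies to person-level covariates only, or restate it for state and local factors with an assumed ICC and number of states.

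The cost is wording and a model option. No new data are needed, since institution and ZIP code are already collected at registration (Section 4.1) and ZIP is available for TMIST participants (Table 1). The downside is wider, correct intervals and lower stated power for state-level factors.

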EAQ201 project manager will create a list of eligible sites based on EA1151 recruitment and enrollment status and will notify CTSU of ECOG-ACRIN clearance of this site qualification criteria. Site submission of required IRB documentation to NCI CIRB will be monitored in RSS weekly by the EAQ201 project manager who will report site activation clearances in CTSU weekly to the EAQ201 study chair by [define weekly communication mechanism you prefer here]. All sites that plan to open EAQ201 are strongly encouraged to activate EAQ201 within 30 days of ECOG-ACRIN activation of the trial as there will be no maximum number of subjects that can be enrolled in the trial at any one site and enrollment is expected to be completed within a few months.

EAQ201 project manager will reach out weekly to all eligible EA1151 sites to remind them about the EAQ201 study and obtain IRB approval through NCI CIRB. This outreach will occur by email to TMIST PI and TMIST lead coordinator until the site opens EAQ201, declines to participate, or EAQ201 enrollment reaches 50% of planned enrollment, 500.

**Participant Recruitment Plan:** All participating EAQ201 TMIST sites will be expected to approach at least 20 women per month in person or over the phone as part of their TMIST recruitment effort while EAQ201 is open to participant enrollment with at least 5 women approached that are classified as Women of Color [definition] according to information documented in the site's electronic medical record system.

All women presenting for screening mammography who meet the eligibility criteria for EA1151 but ultimately decline to participate in EA1151 should be immediately invited to participate in EAQ201 by EA1151 site designated recruiters.

All EAQ201 TMIST sites are expected to keep local TMIST recruitment logs for duration of EAQ201 enrollment period. The first two weeks of local TMIST recruitment logs for each site are to be submitted to the EAQ201 project manager to confirm that recruitment effort is happening for TMIST and to monitor number of WOC TMIST declines at the site. This information will be summarized across all sites for reporting to the EAQ201 central trial team to compare to EAQ201 enrollment rates at each site to determine if site is on track to complete within timeline planned and that overall WOC versus non-WOC participation ratio is within 10%-25% range planned.

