**Survey administration and data collection:** We will use the ECOG-ACRIN Systems for Easy Entry of Participant Reported Outcomes (EASEE-PRO), our online survey platform supplemented by paper and/or telephone surveys using methods successfully employed in EAQ162CD financial burden assessment in colorectal cancer ([name] co-PI) and E4112 prospective study of MRI and multiparameter gene expression assay in DCIS ([name] co-I). Proxies are not allowed to complete questionnaires on behalf of participants. However, participants may use assistance and other accommodations to

complete questionnaires, including: CRAs, participant navigators/advocates, family members, and/or other individuals or aids that allow the participant to understand and record their answers to the survey questions (for example, visually impaired individuals may have questions read to them and their responses recorded). The surveys are available only in English.

TMIST site RAs will collect contact information at EAQ201 enrollment using Participant Contact Information Forms (name, home address, phone number and e-mail) and fax it to the central ECOG-ACRIN OEAU at Brown University. The COVID factors survey may be completed at the screening visit by paper or online. We assume that 40% will opt to complete the survey after the screening visit based E4112 patient preferences. Those who elect to complete the survey after the screening visit will only be able to do so online to conform to the scope of a supplement. These women will receive an invitation and account activation email from the central ECOG-ACRIN Outcomes and Economic Assessment Unit (OEAU) within 7 days to complete the online survey. Each online participant will use a unique account to complete the survey.

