Women who choose to complete their survey online either during or after the screening visit will use our EASEE-PRO web-based participant-facing system. Through EASEE-PRO, study staff communicate with participants about study participation (e.g., email solicitations to logon and complete the survey using unique links and reminders). All study participants can access EASEE-PRO with a valid email address. Upon enrollment into the study, women will be able to activate their account using their email address, either in person or remotely. Activation requires entry of verification information (e.g., DOB) in order to complete activation. TMIST site RAs with the appropriate study roles will be granted access allowing them to assist participants who experience any difficulty. The web site includes a study-specific toll-free phone number to contact OEAU staff for assistance. All data will be stored on a secure server. Participants who do not complete the web surveys within 3 working days of initial e-mail request will receive up to 3 additional e-mail reminders, each 3 days apart. These reminder e-mails provide a link to the current surveys, ask the participant to confirm that they have been able to access the web site and provide both the e-mail address and the toll-free help number for support. All surveys will remain available for participants until either completed or participants are off-study. Since the completion date is recorded for all surveys, the study team will determine appropriate inclusion of these data in specific analyses. If a participant is non-compliant, the OEAU may contact the site CRA and/or the participant in an effort re-establish contact, remove barriers, and obtain the survey responses. These efforts may include email, mail, and phone contact with no more than 3 attempts by any method (i.e., three failed recovery attempts, at least 3 days apart, will be considered participant refusal.)

Women who choose to complete their surveys on paper at the site, should be provided with a paper copy of the survey to complete. The site personnel may then enter the answers into EASEE-PRO. Alternatively, the questionnaire may be faxed to the OEAU. Also, the CRA may have the participant complete the questionnaire on a site-provided tablet or computer.

Outcome and moderator measures are summarized in Table 1 and 2. Participant survey burden in EAQ162CD was 3.25–5.18 questions per minute. The approximately 60 item survey is estimated to take 12-18 minutes.

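### Table 4 treats all 1,000 enrolled women as analysed, so the stated power for the survey-based primary endpoint (77% and 88% in the worked examples) holds only if every survey is completed

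*Combined protocol and SAP*

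**What the plan says.** **The 1,000 is enrolment.** Section 7.2 (Sample Size Considerations) says "At a sample size of 1000 women who decline TMIST participation, we expect to recruit at least 10-25% WOC into this study" and adds that "accruing 1,000 women to this study is achievable". Section 5 stops its weekly site outreach once "EAQ201 enrollment reaches 50% of planned enrollment, 500", so full planned enrolment is 1,000. The accrual table in Section 7.6 also totals 1,000.

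**The same 1,000 is the analysed number in the power calculation.** All 12 rows of Table 4 show N=1000 with a two-sided Fisher's exact test at alpha 0.05. The first worked example, which sets 0.20 in WOC against 0.10 in non-WOC, reads: "at a sample size of 1000 with 10% of WOC, we have 77% power to detect a minimum difference of 0.10 between two proportions". The second gives 88% power for 0.18 vs 0.1 with 25% WOC.

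**The endpoint comes from the survey.** Table 1 defines COVID-related financial hardship entirely by affirmative answers to survey items. The registration list in Section 4.1 contains none of them.

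**Non-completion is foreseen.** On timing, Section 5 says "We assume that 40% will opt to complete the survey after the screening visit", and lets these women respond only online. It provides for reminders and further contact, after which "three failed recovery attempts, at least 3 days apart, will be considered participant refusal". Section 4.3.5 refers to overdue or missing questionnaires. Section 7.5 sets out missing-data methods, and Section 7.2 plans primary results with and without adjustment for missing values. No section gives an expected completion rate, inflates N for loss, or shows power at a reduced N.

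**The concern.** Being registered and having an observed endpoint are different things in this study. A woman can enrol, defer the survey, and be counted a refusal after three failed contacts. She then counts towards the 1,000 but contributes no primary outcome. Power computed on 1,000 is therefore an upper figure, reached only if nobody is lost.

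What is at stake is the accuracy of the planning statement. At 10% WOC the smaller group has only 100 women, and the worked example is already below 80% at full completion, so there is little room for further loss. A reader using Table 4 to judge how informative a null result would be would rely on more information than the design may deliver.

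**Working it through.** **Inputs from the documents.** N=1000; two-sided Fisher's exact test; alpha 0.05; group sizes 100/900 (10% WOC) and 250/750 (25% WOC); the proportions in Table 4.

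**Input that is assumed.** The completion rate c, because the documents give none. It is taken as equal in both groups and shown at 95%, 90% and 80%.

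**Formula.** Let X1 ~ Bin(n1, P1) be the number of WOC with hardship and X2 ~ Bin(n2, P2) the number of non-WOC. Power is the sum of Pr(X1=x1)·Pr(X2=x2) over all pairs (x1, x2) whose two-sided Fisher p-value is at most 0.05. For incomplete surveys, n1 and n2 are replaced by c·n1 and c·n2, rounded to whole women.

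**Step 1: reproduce Table 4 at N=1000.** All 12 rows reproduce within 0.014.
- 100/900, 0.20 vs 0.10: 0.777 (stated 0.77).
- 250/750, 0.18 vs 0.10: 0.886 (stated 0.88).
- Largest gap: 100/900, 0.25 vs 0.15: 0.674 (stated 0.66).

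The normal approximation gives 0.804 for the first of these, so Fisher's test is the method that matches. The stated power therefore needs an observed endpoint from all 1,000 women.

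**Step 2: repeat at reduced completion.**

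| Scenario | Stated | 100% | 95% | 90% | 80% |
|---|---|---|---|---|---|
| 10% WOC, 0.20 vs 0.10 | 0.77 | 0.777 | 0.754 | 0.734 | 0.685 |
| 25% WOC, 0.18 vs 0.10 | 0.88 | 0.886 | 0.872 | 0.851 | 0.809 |

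For the first row the group sizes are 100/900, 95/855, 90/810 and 80/720. For the second they are 250/750, 238/712, 225/675 and 200/600.

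**Step 3: the other ten rows.** Table 4 has nine rows with stated power of at least 0.80, including the 88% example. Eight of the nine remain above 0.80 at 80% completion. The exception is 10% WOC, 0.275 vs 0.15 (stated 0.83), which falls to 0.797 at 90% and 0.751 at 80%. The remaining three rows (stated 0.77, 0.66 and 0.79) were below 0.80 from the start.

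**Step 4: how the 40% enters.** It is the share who complete after the visit. If all other women complete and a fraction f of the deferrers do not, overall loss is 0.40·f. With f from 10% to 50% (an assumption), loss is 0.40·0.10 = 4% to 0.40·0.50 = 20%, which is broadly the range tabulated.

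**The case against.** The strongest reply is that Table 4 contains no error. Its power figures are conditional on a sample size of 1,000, and on that condition they are right. This stands: the point concerns an unstated assumption, not a miscalculation.

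A second reply is that loss should be limited. There is one baseline survey and so no longitudinal attrition; most women are expected to answer at the visit; deferrers get up to three reminders; and Section 4.3.5 allows telephone or mailed-paper follow-up. This also stands as a reason to expect modest loss. It does not make completion 100%, and the plan's own refusal rule says as much.

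A third reply is that Section 7.5 already deals with missing data. Imputation and sensitivity analyses address bias and may recover some information, but they do not justify counting a non-responder as fully observed in a Fisher calculation. Section 7.5 also says only that imputation may be used.

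A fourth reply is that the effect is small beside other uncertainties. For 0.20 vs 0.10, Table 4 itself moves from 0.77 to 0.97 between 10% and 25% WOC. That is fair, and it is why the point is one of reporting rather than of design validity.

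A reader might go further and take the 40% as the expected proportion missing, or conclude that the study is underpowered throughout. The documents support neither. The 40% is a timing preference; 60% completion would require every deferrer to be lost, which nothing in the plan suggests. Most rows also keep power above 0.80 at 80% completion.

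**Conclusion.** The concern holds as an unstated completion assumption. The 77% and 88% figures apply only if all 1,000 enrolled women supply the primary endpoint. At 95% completion the two examples lose about 1 to 2 points against the recomputed full-completion values, at 90% about 4 points, and at 80% about 8 to 9 points. The 88% example stays just above 0.80 (0.81). The 77% example moves further below it (0.69).

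The size rests on assumed completion rates, equal in both groups; only the direction follows from the documents. Lower completion among WOC would cost more, because theirs is the smaller group. With 70% completion in WOC and 90% in non-WOC (again assumed), the examples have power 0.64 (70/810) and 0.79 (175/675).

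This does not invalidate the design or the planned analysis.

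**What to change.** 1. State an expected survey completion rate in Section 7.2, with its basis.
2. Restate Table 4 and both worked examples on expected completed surveys, for example N=900 and N=800, keeping N=1000 only as the full-completion reference.
3. For objective 2.2.3, N=1000 may be kept if race and ethnicity are taken from registration (both are listed in Section 4.1). First reconcile this with Section 5, which describes the sociodemographic comparison with TMIST as using women who complete the survey.
4. Do not state that N=1000 applies to Section 7.4. That model names marital status, which is not among the Section 4.1 registration items, so its analysis set also depends on survey completion.

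The cost is a revised table and a few sentences, with less favourable power figures. Enrolment, the test and the conduct of the study do not change.
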